Appendix 5: Mallampati score

Klasse 1: Udsyn til den bløde gane, drøbelen, mandler og ganebuer,

Klasse 2: Udsyn til den bløde gane og drøbelen samt delvist til mandlerne.

Klasse 3: Udsyn til den bløde gane og den øverste del af drøbelen.

1.1 Confidence intervals and *P* values

The level of statistical significance will be $p < 0.05$ and 95% confidence interval will be reported.

1.2 Adherence and Protocol deviations

Definition of adherence to the intervention

Adherence is defined as participants who has a full registration of identification number (CPR number), test center site for collection of specimen and randomization to control or intervention group. Further, the participants need to complete the OPS specimen collection send for molecular testing.

Compliance is assessed based on the number and percent of subjects who have correct registration information and representative samples for RT-PCR.

Description of adherence

The adherence to the intervention will be summarized in the study flowchart and number and “% compliance” will be summarized.

Definition of protocol deviations for the trial

The participants will be excluded from final analysis if one or more of the following deviations from the testing protocol was found:

Missing identification number (CPR number), no registered test center sites or no randomization (intervention or control) registered.

Missing RT-PCR result

Description of which protocol deviations will be summarized

The number and type of protocol deviation will be registered, and number of participants removed will be summarized in figure with study flow.

2. Trial Population

2.1 Screening data

We aim to invite individuals from Valby and Hillerød Covid-19 test centers to represent citizens from two urban areas in Copenhagen, Denmark to participate in the study.

2.2 Eligibility

All individuals being 18 years or older will be invited to participate in the SAMPLE trial. The same individual will only be allowed to participate in the study once.

The exclusion criteria were individuals with a tracheostomy, laryngectomy, or prior oropharyngeal cancer surgery without a Danish civil registration number (CPR)

2.3 Recruitment

A trial flow diagram will be used to summarize the number of included participants with information about:

- Total number of Covid-19 tested individuals during the study period
- Number of participants lost to identify / registrar
- Number of participants excluded from final analyses due missing test results

2.4 Withdrawal/Follow-up

The level of withdrawal and the missing final RT-PCR test results during the study will be tabulated. As they only had a single OPS performed, no dropouts will be expected after the intervention – beside missing data.

2.5 Baseline patient characteristics

List of baseline characteristics for participants:

Measure	Outcome	Description
Demographic data	Age and gender	Data from the Danish civil registration number
Questionnaire	Test reason, symptom description, vaccination status, prior SARS-CoV-2 infection, prior tonsillectomy	Questionnaire registered in RedCap
NRS-scale	Discomfort score for OPS specimen collections	11-item measure of test-related discomfort answered immediately after testing
Mallampati score	A visual assessment of the distance from the tongue base to the roof of the mouth of the participants	4-item measure of amount of space in the mouth to reach the oropharynx assessed by the healthcare workers

Categorical data will be summarized with number and percentage while continuous data will be summarized by mean and standard deviation. We will not perform tests of statistical significance for baseline characteristics.

3. Analysis

3.1 Outcome definitions

The primary outcome:

- The proportion of positive SARS-CoV-2 RNA samples by RT-PCR for intervention and control group

The secondary outcome:

- SARS-CoV-2 RT-PCR cycle threshold (Ct) value
- Test discomfort on a 11-point NRS-scale
- Development of COVID-19 disease after testing
- SARS-CoV-2 detection rate for each healthcare worker
- Mallampati Score of participants being tested

3.1 Analysis methods

Analysis method and treatment effects

Differences in the proportion of SARS-CoV-2 positive tests between the intervention and the control group will be compared using binary logistic regression using test center as fixed effect and a generalized estimating equation to adjust for clustering of data within the healthcare workers performing the sample. The difference in SARS-CoV-2 detection rate between healthcare workers will also be reported separately to estimate the inter-person variance. The Ct values from positive RT-PCR samples and the NRS discomfort scores will be compared using a general linear model with mixed effects (Ct) and GEE models (NRS discomfort).

The 95% confidence intervals (CI) will be presented. The level of statistical significance will be defined as $p < 0.05$.

Adjustment for covariates

The regression analyses will be adjusted for the effect of the test centers and the individual health-care worker performing the sample.

Methods used for assumptions to be checked for statistical methods

Assumptions for the logistic regression analysis included a binary outcome, independent observations and linearity in logit for continuous variables. To account for lack of independent observations, a generalized estimating equation approach will be applied. No continuous variables will be included.

Assumptions for the linear regression analysis included a normal distribution, independent observations, equal variation (homoscedasticity) and linearity in logit for continuous variables. Normally distributed outcomes and homoscedasticity will be evaluated visually by plots of the residuals. To account for lack of independent observations, a generalized estimating equation approach and mixed effect models will be applied. No continuous variables will be included.

Details of alternative methods to be used if distributional assumptions do not hold, e.g., normality, proportional hazards, etc.

If the assumption of a normal distribution of the outcome in the linear regression model is not fulfilled, a transformation of the outcome will be applied (e.g., logarithmic and rank transformations).

Planned subgroup analyses

We planned to do a sensitivity analysis using a lower cycle threshold (Ct) < 25 for positive SARS-CoV-2 definition to explore the consequences of a higher test specificity for the SARS-CoV-2 detection rate between specimen types. We also plan to estimate the sensitivity and specificity using Bayesian latent class analysis for accounting for an imperfect reference standard. Further, we planned to do subgroup analyses exploring the distribution of positive test results for participants stratified by symptoms, previous COVID-19 infection, vaccinations status, prior tonsillectomy and Mallampati score. To explore a potential bias from the distribution of the inconclusive test results, we excluded the inconclusive results in a subgroup analyses.

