After enrollment, the participants will be randomized in a 1:1 ratio having either oropharyngeal swab performed including the posterior oropharyngeal wall and both palatine tonsils (intervention group) or only including the posterior oropharyngeal wall and avoiding the palatine tonsils (control group), see Figure B.

A block randomization list was generated by [name] using an online randomization software⁽⁷⁾ afterward uploaded to REDCap. The randomization group will be disclosed in connection with trial registration in REDCap using the REDCap “randomize” function. The oropharyngeal sample will afterward be performed by the trained healthcare workers with or without the palatine tonsils depending on the randomization to either the intervention or control group.

Figure B. Study flowchart.

The swabs will be placed in separate tubes dry and sent to the clinical microbiology laboratory for detection of SARS-CoV-2 by single-target RT-PCR at Statens Serum Institute. Samples with viral cycle threshold (Ct) values below 38 are considered positive, 38-40 inconclusive and above 40 negative⁽⁸⁾.

All participants are required to fill out a survey on-site about their reason for being tested, prior Covid-19 infection(s), vaccinations status, symptoms, and if any prior tonsillectomy has been performed (appendix 2).

All healthcare workers participating in the data collection have been given a unique ID which will be registered for each OPS performed in the study. Further, the healthcare worker will also be asked to rate the Mallampati score of the participants including in the study (appendix 5).

All data will be documented on-site in a secure web database (REDCap, appendix 3).

Outcomes

The primary outcome will be reported as:

- SARS-CoV-2 RNA by RT-PCR test result (positive, negative, inconclusive)

The secondary outcome will be reported as:

- SARS-CoV-2 RT-PCR cycle threshold (Ct) value
- Test discomfort on a 11-point NRS-scale
- Development of COVID-19 disease after testing
- SARS-CoV-2 detection rate for each healthcare worker
- Mallampati Score of participants being tested

Sample size

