Based on a SARS-CoV-2 test positive proportion on 13% in the Danish capital region the last week of October 2022, we expected proportion of positive to increase to about 20% during the following study period⁽⁹⁾. The power calculation was based on an expected improvement in diagnostic accuracy of 25% by including the palatine tonsils in the oropharyngeal specimen collection compared to a sample without the tonsils. We therefore estimated that a sample of 2,188 participants (with about 438 with SARS-CoV-2 infection) would provide the trial with 80% power at a 5% significance level with an expected test positive proportion of 20% for SARS-CoV-2

among the participants tested ⁽¹⁰⁾. As we expect about 10% missing due to dropout and missing data, we aim to include 2,407 participants in the study. All individuals entering the testing facility who meet the eligibility criteria are offered to participate in the study. We expect about 300-700 tests performed at both COVID-19 test centers each day and an assumed participation at 10-30%. We therefore expect to complete the study within two-three months.

Statistical analysis

A study participant is considered to have a SARS-CoV-2 infection if the oropharyngeal sample is RT-PCR positive (reference standard). Participants with an inconclusive RT-PCR test result will be included in the analyses as a negative test result following an intention-to-diagnose approach⁽¹¹⁾. Differences in the proportion of SARS-CoV-2 positive tests between the intervention and the control group will be compared using binary logistic regression using test center as fixed effect and a generalized estimating equation to adjust for clustering of data within the healthcare workers performing the sample. The difference in SARS-CoV-2 detection rate between healthcare workers will also be reported separately to estimate the inter-person variance. The Ct values from positive RT-PCR samples and the NRS discomfort scores will be compared using a general linear model with mixed effects (Ct) and GEE models (NRS discomfort). The 95% confidence intervals (CI) will be presented. Categorical data will be summarized with number and percentage while continuous data will be summarized by mean and standard deviation. We will not perform tests of statistical significance for baseline characteristics. 5% significance level was applied. Statistical Analysis Software ver. 9.4 (SAS Institute, North Carolina, U.S.) was used for the statistical analyses.

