Planned subgroup analyses

We planned to do a sensitivity analysis using a lower cycle threshold (Ct) < 25 for positive SARS-CoV-2 definition to explore the consequences of a higher test specificity for the SARS-CoV-2 detection rate between specimen types. We also plan to estimate the sensitivity and specificity using Bayesian latent class analysis for accounting for an imperfect reference standard. Further, we planned to do subgroup analyses exploring the distribution of positive test results for participants stratified by symptoms, previous COVID-19 infection, vaccinations status, prior

tonsillectomy and Mallampati score. To explore a potential bias from the distribution of the inconclusive test results, we excluded the inconclusive results in a subgroup analyses.

Quality assurance

All the healthcare workers who will be including participants for this study will be trained and have at least three months prior experience in oropharyngeal swabs. Further, they will complete a special standardized training- and certification program taught by a board-certified otorhinolaryngologist to ensure all healthcare workers perform the same technique on the participants in the intervention and control group. A two-hour long training session will cover the theoretical and practical part of oropharyngeal sample techniques and the study design with following elements:

- A walk-through of the practical study setup and how participants are enrolled, and diagnostic interventions are performed
- Theory on oropharyngeal swabbing including upper airway anatomy and anatomical variations/Mallampati Score.
- Practical exercises in oropharyngeal swab technique.

Checklists outlining the two different sampling techniques for oropharyngeal swabs with and without palatine tonsils, respectively, will be used to assess the swab performance of all the healthcare workers by a board-certified otolaryngologist or special trained nurse before study enrollment (see appendix 1).

An on-site healthcare professional is in charge of internal daily quality assurance ([name]).

Follow-up

The participants enrolled in the study will be asked to agree to be contacted in case of a positive test result. About one month after a positive test results the participants will receive an online questionnaire or phone call to follow up. The follow-up questions can be found in appendix 3.

Ethics and safety considerations

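### Ct values are compared between arms only among RT-PCR-positive samples, although positivity is the primary outcome and is planned to differ by arm

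*Combined protocol and SAP*

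**What the plan says.** Ct is a listed secondary outcome (protocol, Outcomes; SAP 3.1, Outcome definitions). Both analysis sections limit its comparison to positives. The SAP states: "The Ct values from positive RT-PCR samples and the NRS discomfort scores will be compared using a general linear model with mixed effects". The mixed model is for Ct, and GEE is for the discomfort score. The protocol's Statistical analysis section has the same sentence.

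In the same SAP section, "The 95% confidence intervals (CI) will be presented", and "The level of statistical significance will be defined as" p < 0.05. No comparison is exempted from either statement.

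The definition of a positive sample is in the protocol, under Randomization to intervention and control group: "Samples with viral cycle threshold (Ct) values below 38 are considered positive, 38-40 inconclusive and above 40 negative".

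The primary outcome is the proportion positive by arm. The Sample size section powers the trial on an "expected improvement in diagnostic accuracy of 25% by including the palatine tonsils in the oropharyngeal specimen collection", with 20% positive as the planning rate.

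The only stated adjustments are for test center and healthcare worker. The closest related analysis, under Planned subgroup analyses, is a "sensitivity analysis using a lower cycle threshold (Ct) < 25 for positive SARS-CoV-2 definition".

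**The concern.** Randomisation makes the two arms comparable as whole groups. It does not make the positives in one arm comparable with the positives in the other, because being positive is itself a result of the technique under test. If the tonsil swab detects more infections, its positives include people whom the control swab would have missed, and the two Ct sets then represent different people.

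A Ct difference with a confidence interval and a p-value is easily read as showing how much virus each technique collects. Two mechanisms lead to different readings:

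- If the tonsil swab lowers everyone's Ct, the positives-only difference points the right way but is too small.
- If it mainly adds infections with high Ct, a real benefit can be masked or appear reversed.

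Mean Ct among positives cannot show which of these has happened. Nothing in the plan labels the comparison as conditional or corrects for the selection. The logarithmic and rank transformations named as fallbacks would act on the same selected set.

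**Working it through.** **1. The planned rates.** Inputs from the protocol's Sample size section: 20% positive, 25% improvement, 80% power, 5% significance. Allocation is 1:1. The 25% arm rate is not printed; reading the improvement as relative gives 0.20 × 1.25 = 0.25. The two-sided pooled formula is

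n = [1.96 √(2 × 0.225 × 0.775) + 0.842 √(0.20 × 0.80 + 0.25 × 0.75)]² / 0.05² = 1,093.7, so 1,094 per arm and 2,188 in total.

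This matches the plan exactly. Other readings do not: one-sided gives 1,724, continuity-corrected 2,268, 16% versus 20% gives 2,894, and 15% versus 20% gives 1,812.

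**2. The Ct sets at those rates.** Control: 0.20 × 1,094 = 219. Intervention: 0.25 × 1,094 = 274. If the tonsil swab detects everyone the control swab would, the extra positives number 274 − 219 = 55, and 55/274 = 20%.

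The remaining steps need Ct means, SDs and sensitivities. The documents give none, so those values are assumptions.

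**3. Uniform fall in Ct.** Take Ct in infected people as normal with standard deviation SD, and positive if below 38. For sensitivity s, the mean is m = 38 − SD·z(s), and the mean among positives is m − SD·φ(z(s))/s. Sensitivity rises by a factor of 1.25. The table uses SD 5.

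| Sensitivity, control to tonsil | True shift | Shift among positives | Ratio |
|---|---|---|---|
| 60% to 75% | −2.11 | −1.00 | 0.48 |
| 64% to 80% | −2.42 | −1.24 | 0.51 |
| 72% to 90% | −3.49 | −2.13 | 0.61 |

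SD multiplies both shifts, so the ratios do not depend on it.

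**4. Extra positives only.** Leave every other Ct unchanged and place the extra 20% at Ct = x. The difference in means is 0.2 × (x − control mean among positives).

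| SD, control sensitivity | Control mean | x = 33 | x = 35 | x = 37 |
|---|---|---|---|---|
| 5, 60% | 33.51 | −0.10 | +0.30 | +0.70 |
| 5, 72% | 32.75 | +0.05 | +0.45 | +0.85 |
| 7, 60% | 31.72 | +0.26 | +0.66 | +1.06 |
| 7, 72% | 30.65 | +0.47 | +0.87 | +1.27 |

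At SD 5 and 72%, the SD among positives is 3.57. Ignoring clustering, the 95% CI half-width is 1.96 × 3.57 × √(1/219 + 1/274) = 0.63.

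In that setting, suppose Ct also falls by f in the other 80% of intervention positives. The mean difference is zero when 0.8f = 0.2(x − 32.75), so f = 0.25(x − 32.75). That is 0.56 cycles at x = 35 and 1.06 at x = 37: real falls of that size would vanish.

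**5. Trimming bounds.** Discard either the highest or the lowest 20% of intervention Ct values, taking Ct among positives as normal. The intervention mean moves by φ(z(0.8))/0.8 = 0.280/0.8 = 0.35 SD each way. With an SD among positives of 4 to 7, this is 1.4 to 2.4 cycles, against standard errors of 0.36 to 0.63, or about 3.9 standard errors. Selection uncertainty on this reckoning is well beyond what the planned interval expresses.

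**6. Whether thresholds can separate the mechanisms.** Take SD 5, sensitivity 72% to 90%, and prevalence 0.20/0.72. The denominators are all participants with a result.

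| Cut-off | Control | Tonsil, uniform fall | Tonsil, only Ct 33–37 cases added |
|---|---|---|---|
| Ct < 30 | 4.3% | 10.4% | 4.3% |
| Ct < 38 | 20% | 25% | 25% |

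The two mechanisms give the same result at 38 and clearly different results at 30.

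**The case against.** The strongest reply has four parts.

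- **The problem is conditional.** If both swabs detect the same people there is no bias, and if technique changes nothing the test holds its 5% level. This is true, but the trial is designed on the opposite expectation.
- **The size is assumed, and the harmful cases are particular.** Under a uniform fall, the error is only attenuation. With extra positives at Ct 35, the spurious difference stays below the CI half-width in every combination tried (SD 4 to 7, control sensitivity 60%, 64% and 72%); at SD 5 and 72% it is +0.45 against 0.63. It exceeds the half-width only when the extra positives lie nearer the cut-off, such as Ct 37. The threshold contrast is also weaker in other settings: at 60% to 75% and SD 5, Ct < 30 is 3.0% versus 5.9%. All of this stands. It limits the size of the problem but does not make the comparison randomised.
- **The plan discloses the restriction and already has an unselected analysis.** The wording does say that Ct comes from positives, and the Ct < 25 analysis keeps the full denominator. That analysis is motivated by specificity, however, and does not replace or qualify the Ct difference. It may also be thin: the SD 5, 72% model gives only about 7 of 1,094 controls below 25.
- **It is one of five secondary outcomes, and more thresholds mean more looks.** Both are fair points. They argue for a light remedy with exploratory labelling.

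**Conclusion.** The concern holds. The planned Ct comparison conditions on a post-randomisation result that is the primary outcome and is powered to differ between arms. Nothing in the plan corrects for this or warns the reader.

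The planned rates, the exact match to 2,188 and the 20% of intervention positives without a counterpart follow from the documents' figures; the last also assumes that the tonsil swab loses no positives. The size and direction of the bias do not. Under the assumptions shown, a uniform fall in Ct appears at 48% to 61% of its true size, and extra positives alone shift the difference by −0.1 to +1.3 cycles. The problem disappears if the two techniques detect the same people.

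The primary comparison and the sample size are not affected. The change is worth making because a reported Ct difference could otherwise be taken as evidence on sampling efficiency that it cannot supply.

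**What to change.** In the protocol's Statistical analysis section and SAP 3.1 (Analysis methods), state that mean Ct among positives is descriptive and conditional on detection, and that no inference about sampling efficiency will be drawn from it.

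As the between-arm Ct analysis, report the proportion below several pre-specified cut-offs (for example 25, 30, 35 and 38) by arm. Use all randomised participants with an RT-PCR result as the denominator, and the GEE logistic model already planned. This extends the existing Ct < 25 analysis.

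The thresholds are correlated and low cut-offs may have few events, so present them as exploratory, with confidence intervals. A rank analysis with negatives tied at the worst value is possible, but largely repeats the primary comparison.

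The cost is a few sentences and a few more runs of a planned model on Ct data already collected. No new participants, contacts or data are needed.

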Appendix 2: Survey for participants

Survey to be filled out by participant

1. Are you vaccinated against COVID-19?

YES

NO

2. Have you previously been infected with COVID-19?

YES

NO

3. Please indicate your reason for getting tested today:

Symptoms

Close contact

Positive quick test

Screening

Test ahead of social gathering or nursing home visit

Other

If 'yes' to symptoms, which symptoms do you have?

Sore throat

Headache

Cough

Muscle and joint pain

Fever

Fatigue

Reduced sense of smell or taste

If "yes" to symptoms, for how many days have you had symptoms?

Indicate number of days: _____ day(s)

4. Have you had your tonsils removed??

YES

NO

5. On a scale from 0-10, how uncomfortable was today's test for COVID-19?

No discomfort

Worst possible discomfort

To be filled out by personnel:

REDCap ID: _____

Personnel ID: _____

Participant's Mallampati score:

1

2

3

4

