Appendix 3: REDCap database

REDCap-ID	
Date	DD-MM-YYYY
Randomization	Oropharyngeal swab including palatine tonsils Oropharyngeal swab excluding palatine tonsils
CPR-number	
Sample ID	
Are you vaccinated against COVID-19?	YES NO
Have you previously been infected with COVID-19?	YES NO
Please indicate your reason your reason for getting tested today	Symptoms Close contact Positive quick test Screening Test ahead of social gathering / visit to a nursing home Other
If "YES" to symptoms, what symptoms do you have?	Sore throat Headache Cough Muscle and joint pain Fever Fatigue Reduced sense of smell or taste
If "YES" to symptoms, for how many days have you had symptoms?	
Have you had your tonsils removed?	YES NO
On a scale from 0-10, how uncomfortable was today's test for COVID-19?	0 1

	2 3 4 5 6 7 8 9 10
Personnel ID	
Participant's Mallampati score	1 2 3 4
FOLLOW UP	
Have you since the test and until four weeks later had symptoms of COVID-19?	YES NO
If 'yes' to symptoms, when did you develop symptoms?	I had symptoms when I got tested I developed symptoms 1-3 days after the test I developed symptoms 3-5 days after the test I developed symptoms 5-7 days after the test I developed symptoms 1-2 weeks after the test I developed symptoms 2-3 weeks after the test I developed symptoms 3-4 weeks after the test I do not know / I do not wish to disclose
If 'yes' to symptoms, which symptoms did you develop?	Sore throat Headache Cough Muscle- / joint pain Fever Fatigue Reduced sense of smell / taste Other
If 'yes' to fever, what was your highest temperature?	

If 'yes' to fever, how many days did you have a fever for?	
If 'yes' to symptoms, how many days did you have symptoms in total?	
Think about period from one week before your test until four weeks after. Which of the following statements describes best how you felt at your worst?	
I had no symptoms
 
I was sick and stayed home
 
I was admitted to the hospital due to COVID-19

Have you taken days off work / from school during your infection with COVID-19?	
No, I have not taken any days off
 
Yes, I have taken days off between one week before the test until four weeks after
 
Yes, I have taken days off later than four weeks after
 
Not relevant

If 'yes' to having taken days off, how many days have you taken off in total?	
Do you smoke?	
Yes
 
No
 
I used to smoke, but I do not smoke anymore
 
Not relevant / I do not wish to disclose

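### Optional improvement: the primary model could adjust for reason for testing, which the required on-site survey already records; the gain may be negligible or worthwhile

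*Combined protocol and SAP*

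**What the plan says.** The primary comparison is a logistic GEE with test centre as a fixed effect and clustering on healthcare worker. The protocol (Statistical analysis) and the SAP (3.1 Analysis methods) agree on this. The SAP's paragraph on covariates reads: "The regression analyses will be adjusted for the effect of the test centers and the individual health-care worker performing the sample".

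The protocol (Randomization to intervention and control group) says: "All participants are required to fill out a survey on-site about their reason for being tested". The item in Appendix 2 is "Please indicate your reason for getting tested today", with six options that include "Positive quick test", symptoms and close contact. There is no separate symptom question. Symptom type and duration follow only if symptoms is ticked as a reason; the database in Appendix 3 has the same conditional item, "to symptoms, what symptoms do you have".

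SAP 2.5 lists these questionnaire items as baseline characteristics: "Test reason, symptom description, vaccination status, prior SARS-CoV-2 infection, prior tonsillectomy". Symptoms otherwise appear only as a stratifying factor in the planned subgroup analyses of both documents. SAP 3.3 keeps participants with missing questionnaire data in the primary analysis.

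On timing, the protocol says: "The randomization group will be disclosed in connection with trial registration in REDCap". The same survey form carries the discomfort item, which SAP 2.5 describes as "11-item measure of test-related discomfort answered immediately after testing".

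**The concern.** Someone who comes because of a positive quick test or symptoms is plausibly much more likely to have a positive RT-PCR than someone who comes for screening. If so, reason for testing explains part of the variation in the primary outcome, and using it would narrow the confidence interval for the difference in proportions at no cost in data collection.

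The design has little spare power. It assumes that positivity rises from 13% to 20%. At 13% with the same relative gain (13% v 16.25%), power with 1,083 per arm is about 57% by the formula under the working. Precision from data already collected would be useful there.

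**Working it through.** **1. The plan's own figure.** Inputs from the protocol (Sample size): 20% positive, a 25% improvement read as relative (20% v 25%), 80% power, 5% significance. Two-sided testing is assumed.

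n per arm = [1.960·√(2·0.225·0.775) + 0.842·√(0.20·0.80 + 0.25·0.75)]² / 0.05² = (1.1575 + 0.4961)² / 0.0025 = 1,093.7, so 1,094 per arm and **2,188 in total**. This matches and uses no covariate.

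**2. Starting point.** 2,407 less 10% is 2,166, or 1,083 per arm. Power = Φ[(0.05·√1,083 − 1.1575)/0.5895] = Φ(0.828) = 79.6%. The 95% CI half-width for the risk difference is 1.96·√(0.3475/1,083) = 3.51 percentage points.

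**3. Gain by explained variance.** If reason explains a share R² of outcome variance, the half-width shrinks by √(1−R²), and 1,083 per arm acts like 1,083/(1−R²).

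| R² | Power |
|---|---|
| 0% | 79.6% |
| 1% | 80.0% |
| 5% | 81.6% |
| 10% | 83.6% |
| 20% | 87.6% |
| 30% | 91.5% |

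**4. Simulation of the proposed analysis** (4,000 trials per setting for power and 4,000 under the null; N = 2,166; 20% v 25% overall; no worker clustering). All inputs on reasons are assumptions:
- Symptoms in about half of participants, close contact in 25%, and 5% of forms missing (own category).
- Conditional odds ratios for quick test, symptoms and close contact of 20, 2.5 and 1.5 in the first four rows.
- No quick tests, 2.0 and 1.3 in the fifth row.
- 2.5, 1.4 and 1.2, with 2% quick tests, in the last row.

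| Assumed setting | Power, centre only | Power with reasons | Half-width (from 3.51) | SE of log odds ratio (from 0.104) |
|---|---|---|---|---|
| 15% quick tests | 79.5% | 91.0% | 2.94 | 0.125 |
| 10% quick tests | 79.6% | 88.2% | 3.08 | 0.119 |
| 5% quick tests | 79.2% | 85.0% | 3.26 | 0.112 |
| 2% quick tests | 80.6% | 82.8% | 3.37 | 0.108 |
| No quick tests | 79.6% | 80.7% | 3.47 | 0.105 |
| Weak predictors | 79.0% | 79.9% | 3.49 | 0.104 |

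Adjusted type I error was 4.7–5.5%. If only one reason can be ticked, power changes by at most 1.0 point. With no association at all, a separate run at N = 2,188 gave 80.4% with and without adjustment.

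The last column shows why the effect measure matters. The interval narrows for the standardised risk difference. The adjusted odds ratio is conditional, and its log does not gain precision.

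**5. Side note on the GEE variance.** The documents state neither the estimator, the working correlation nor the number of workers. Simulations assumed a worker SD of 0.3 on the logit scale and the same arm effect for all workers.
- Uncorrected sandwich with a normal reference: type I error about 11% with 8 workers, 8–10% with 12, about 7% with 20 (9% with unequal workloads) and about 6% with 40.
- Mancl-DeRouen correction with a t reference on workers minus 2: 3.0–5.1%, but centre-only power of 58–59% with 8 workers.
- Worker fixed effects with model-based errors: type I error 5.7/5.0/5.9% and power 79/79/79% with 8/12/20 workers.

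**The case against.** The strongest reply is that choosing covariates is a matter of preference. The model is pre-specified, both documents agree on it, and randomisation makes it valid. That stands, and it is why this is an option only.

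Second, every gain well above 1 point comes from an assumed odds ratio of 20 for a positive quick test. The documents give neither that figure nor the share who would tick the box. This also stands: the sponsor gets a range, not an expected value.

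Third, symptoms already feature in the planned subgroup analyses. True, but subgroup tables add no precision to the primary comparison.

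Fourth, the reason may be written down after allocation is known, because the form also holds a post-swab item and the paper surveys may be entered later (protocol, Data plan). The reason itself precedes randomisation and the RT-PCR result, so it can be treated as baseline. The risk that knowing the allocation colours the answer remains, and favours recording it first.

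A reader might infer more: that the planned analysis is biased or underpowered without this covariate, or that its test exceeds the 5% level. The documents support neither. The sample size reproduces with no covariate, and inflation would need both an uncorrected sandwich and few workers, neither of which is stated. Nor does it follow that a small-sample correction should be prescribed, given its cost in power when workers are few.

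**Conclusion.** A cheap improvement is available; the plan is not in error. With 2,166 analysed, adjusting for recorded reason for testing would take power from about 80% to somewhere between 80% and 91%. The gain is about 1 point with weak predictors or no quick tests, and about 11 points with 15% quick tests and an odds ratio of 20.

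The prevalence of each reason and its link to positivity are assumed throughout. The firm conclusions are qualitative: the item is collected, it precedes randomisation, it plausibly predicts the result, and adjusting for it does no material harm if it does not. The covariate is the recorded reason for testing, not symptom status, because the form does not ask everyone about symptoms separately.

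The GEE variance is a missing detail to be stated, not a demonstrated problem.

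**What to change.** 1. In SAP 3.1 (Analysis methods), pre-specify indicator terms for positive quick test, symptoms and close contact in the primary logistic GEE. Add a missing category, so that nobody is dropped and SAP 3.3 is still followed.
2. Report the standardised risk difference or ratio as the effect measure. This fits the primary outcome in the SAP's outcome definitions, which is a proportion per arm. Keep the centre-only model as supportive.
3. State that the reason is treated as a pre-randomisation fact. Preferably have it completed before allocation is shown.
4. Add one sentence giving the GEE variance estimator, working correlation and number of workers. If workers are few, do not rely on the uncorrected sandwich. Worker fixed effects with model-based errors are one alternative, provided that workers swab in both arms and the arm effect does not vary between workers.

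**Cost.** Items 1, 2 and 4 need SAP wording and somewhat more analysis code, with no new data. Recording the reason first (item 3) changes site workflow, because one form holds both that question and the post-swab item. The downsides are a possibly negligible gain, a change in the reported effect measure, and reliance on a self-reported item that may be written after allocation is known.
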